Insulin titration per CGM			X	X	X	X	X	X	X	X	X	X	X	X	X
Dispense new CGM sensor			X	X	X	X	X	X	X	X	X	X	X	X	
Dispense study medication		X	X	X	X	X	X	X	X	X	X	X	X	X	
Review of medication adherence					X			X			X				X
Review of co-administered drugs	X	X			X			X			X				X
Lifestyle and behavior counseling		X			X			X			X				X

Highlighted "X" will be done in the Clinical Research Unit. Non-highlighted X will be done in the Delaware Clinical Research Center

a Including height and weight at Weeks 0, 12, 24, 36 and 52. Weight only will be done at Weeks 4, 8, 16, 20, 28, 32, 40, 44, 48. Weight done remotely via Bluetooth monthly if there are no in-person visit scheduled for weeks 28, 32, 40, 44, and 48.

b Blood will be drawn during the OGTT at baseline, 30-, 60-, 90- and 120-minutes following glucose ingestion

c Continuous glucose monitoring with CGM data will be reviewed with participant via telephone after upload by PI or [name], Clinical Diabetes Educator.

d Urine pregnancy tests will be done on all females of childbearing potential. Tests will be done at in-person or at home.

\$ Visit windows for Weeks 4-52 are +/-7 days from the baseline visit

% In-person visits

5.2 Study Procedures:

Physical exam: A study physician will conduct a physical examination to ensure the participant is healthy enough to enroll in the study. A pubertal status will also be undertaken by the study physician ([name]) who is a trained pediatric endocrinologist. She has been trained in the proper technique to assess pubertal stages and will be the same study physician conducting all assessments throughout the trial.

Vital signs: Blood pressure (BP) and heart rate (HR) will be collected.

Hemoglobin A1c: Blood will be collected for a hemoglobin A1c level.

EKG: Electrocardiogram will be performed at screening/baseline visit and per PI discretion.

Eating Disorder Examination Questionnaire (EDE-Q): The EDE-Q identifies disordered eating behaviors and unhealthy attitudes about weight, such as purging, unhealthy obsession with dieting and/or body weight, prolonged fasting/starvation, use of laxatives to control weight and excessive exercise.

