Patient Health Questionnaire-9 (PHQ-9): The PHQ-9 measures depression and suicidality. The PHQ-9 Modified for Teens will be administered to participants < 18 years of age. A participant will be referred to a mental health professional or primary care provider if s/he has a PHQ-9 score of  $\geq 10$  or reports any suicidal behavior. A PHQ-9 score  $\geq 15$  at the screening vision is an exclusion criteria.

Columbia-Suicide Severity Rating Scale (C-SSRS): The C-SSRS measures depression and suicidality. A participant will be referred to a mental health professional or primary care provider if s/he has any suicidal behavior or any suicidal ideation of type 4 or 5 on the C-SSRS. Please see Exclusion Criteria for cut-off scores related to the C-SSRS.

Pediatric Quality of Life Inventory (PedsQL™): The PedsQL measures general and disease-specific quality of life. We will be using the participant-reported measures for the PedsQL™ Generic Core Scales and Diabetes Module Version 3.2 for young adults (aged 18-25 years) and Teens (12-18 years).

Oral Glucose Tolerance Test (OGTT): Insulin sensitivity and  $\beta$ -cell function will be measured via a 2-hour, 75 mg oral glucose tolerance test. OGTT has been widely used in the evaluation of  $\beta$ -cell dysfunction and T2D, including in the TODAY and RISE studies. The OGTT will be performed following a 10-12 hour overnight fast. Participants will take their last dose of metformin (if applicable) the evening before testing. Participants on basal or bolus insulin will be asked to withhold insulin dose either 36 hours or 6 hours, respectively, prior to testing. Plasma glucose levels, C-peptide, and insulin levels will be measured at baseline, 30, 60, 90 and 120 minutes following standard glucose ingestion. If a participant comes to a visit and has not withheld insulin for the required number of hours, the visit

will proceed without the OGTT and the participant will be asked to return to perform the OGTT within one week of the originally scheduled visit.

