Glycemic Control: Time in range (BG of 70-180 mg/dL) and hypoglycemic events will be measured using Continuous Glucose Monitors, either Freestyle Libre 14 day or Dexcom G7. The Freestyle Libre 14 day is no longer being produced so we will phase in the use of Dexcom G7 CGM. Worn on the skin, the disposable, single use sensor will continually measure glucose levels from the interstitium, every minute for 14 days (Libre) or 10 days (Dexcom G7) and will upload the data for review, and the participant will be asked to share this data with the study team. Participants will be taught how to place and replace the CGM. Participants who have a Libre CGM will be instructed to swipe the sensor at least twice daily (fasting and at bedtime) and to upload their CGM data monthly. Participants who have the Dexcom CGM will not need to swipe, but will be instructed to upload their CGM data monthly. CGM data will also be used to titrate insulin and metformin dosing. Percent time of CGM use will be used to assess adherence.

Total daily insulin dose: For participants on insulin therapy, total daily insulin dose (units/kg/day) will be averaged over the previous month at each study visits. Participants will log their insulin doses and return pens to study visits.

Body composition: Total body and visceral fat (% and kg) and measures of bone mineral density will be measured by dual energy x-ray absorptiometry (iDXA). iDXA measurements, using standard positioning techniques, will be conducted and analyzed by trained staff.

Anthropometrics: Height and weight will be collected by trained research staff at weeks 0, 12, 24, 36 and 52. Weight only will be collected at Weeks 4, 8, 16, 20, 28, 32, 40, 44, and 48. Weight will be collected via a scale provided to the participants and reported directly to the research coordinator at Week 28, 32, 40, 44, and 48 if there no monthly visits and per the PI's discretion.

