**Insulin:** Participants may already be on insulin therapy upon enrollment in the study or it may be used to treat hyperglycemia. There is a risk of bruising, bleeding and infection associated with insulin injection. Hypoglycemia may also occur with insulin use, and this risk increases with weight loss. Participants who are on insulin will be trained on the signs of low blood sugar and how to treat an episode of hypoglycemia. Hypoglycemic episodes will be documented by CGM and reviewed monthly, or sooner if needed. Doses of metformin and insulin (if applicable) will be down titrated to help prevent further hypoglycemia.

**Metformin:** Participants may already be on metformin therapy upon enrollment into the study or the metformin dose may be titrated during the course of the study. Side effects of metformin include diarrhea, bloating, nausea and vomiting, which are usually self-resolving. Side effects will be reviewed at each study visit and metformin can be down titrated or discontinued if warranted by the PI. Participants can be on either immediate-release or extended-release formulations of metformin.

**OGTT:** There is a minimal risk of bruising, bleeding and infection associated with the blood draw and peripheral IV placement for the OGTT. There is also a risk of temporary hyperglycemia during the testing.

**Continuous Glucose Monitoring:** There is a minimal risk of bruising, bleeding, and infection associated with placement of the CGM device. Participants will be trained how to apply the device at baseline. In general, CGM is well tolerated and accepted. A diabetes clinical nurse will be available to participants to help address any issues with CGM placement and maintenance remotely.

**Screening and monitoring labs:** The risks of drawing blood for this test include bruising, bleeding and infection at the site where the needle enters the skin. On rare occasions, fainting may occur.

Dual Energy X-ray Absorptiometry (iDXA): The iDXA scans involve exposure to a very low dose of ionizing radiation to generate their picture. The average amount of radiation that the average person would receive from the iDXA scans in this study is less than 1% (3 mrem) of that received from natural sources of radiation by a Minnesota resident in one year (300 mrem).

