### 14.3 Statistical Analysis:

Descriptive analyses of baseline characteristics and outcomes will include means and standard deviations, median and range for continuous variables and frequencies for categorical variables. Treatment adherence will also be evaluated by the methods described above. Safety analyses will be primarily descriptive reporting the number and percentage of adverse events. All safety outcomes will be evaluated and monitored throughout the trial. Confidence intervals (CIs) and p-values will be based on robust variance estimation. Statistical significance will be considered as  $p < 0.05$ .

Aim 1: The primary analysis will be conducted using the ITT population to compare the mean BMI percent change (primary outcome measure) from randomization to 6 months of follow-up between the groups, adjusted for BMI at randomization for added precision. We hypothesize that with participants treated with PHN/TPM will demonstrate greater BMI percent change compared to controls at 6 months. Supportive analyses using the PP population will also be conducted along with consideration of adjustment for residual imbalances

between treatment groups after randomization (e.g., in sex as a biological variable). Longitudinal analyses will also be conducted, incorporating the multiple time points through the open-label extension (6 months to 12 months follow-up) during which these BMI measurements will be obtained. This will examine durability of changes observed over the masked portion of follow-up, as well as provide additional safety information. Supportive analyses using the PP population will also be conducted.

Aim 2: Secondary outcomes will be analyzed in the same fashion as the primary endpoint wherein analyses will be adjusted for values at randomization. Outcome measures for Aim 2 are c-peptide index ( $\Delta C_{30}/\Delta G_{30}$ ), insulin sensitivity (1/fasting insulin),  $\beta$ -cell function relative to insulin sensitivity (oral disposition index [oDI]), A1c (%), and total daily insulin dose (units/kg/day). We hypothesize that participants treated with PHN/TPM will demonstrate improved insulin sensitivity and  $\beta$ -cell function compared to those assigned to placebo as measured by OGTT, A1c and total daily insulin doses. Complementary secondary analyses will also be conducted for each secondary outcome as described for the primary outcome.

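### Section 5.2 states the OGTT glucose load as 75 mg, which does not fit the Aim 2 c-peptide index or the paragraph's own description of the test

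*Combined protocol and SAP*

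**What the plan says.** Section 5.2 (Study Procedures, Oral Glucose Tolerance Test) has insulin sensitivity and β-cell function "measured via a 2-hour, 75 mg oral glucose tolerance test". Later in the same paragraph, plasma glucose, C-peptide and insulin are to be "measured at baseline, 30, 60, 90 and 120 minutes following standard glucose ingestion".

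No other part of the available text gives an amount. Footnote b to the Schedule of Events repeats the sampling times without a load: "Blood will be drawn during the OGTT at baseline, 30-, 60-, 90- and 120-minutes following glucose ingestion". Section 8.3 places the test at the baseline, week 24 and week 52 visits, also without a load.

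Two other sections depend on what the test does:

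- **Section 14.3, Aim 2.** The list begins "Outcome measures for Aim 2 are c-peptide index", defined there as ΔC30/ΔG30. It continues with 1/fasting insulin, the oral disposition index (oDI, no formula given), A1c and total daily insulin dose.
- **Section 12.1, OGTT risks.** "There is also a risk of temporary hyperglycemia during the testing".

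**The concern.** The load is the defining quantity of an OGTT, and Section 5.2 is where staff, monitors and later readers of the methods would look for it. The c-peptide index is a ratio whose denominator is the glucose rise that the load provokes. If the load is too small to provoke one, the denominator is little more than assay error and spontaneous drift. The ratio can then take either sign and any size.

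β-cell function is part of the purpose in Section 1.1 and of the secondary endpoint in Section 3.2, and the test is repeated at three visits. The load must also be the same at each visit for changes from baseline to be comparable. As the text stands, giving any other amount is on paper a departure from the protocol, and Section 17.1 provides for monitoring of deviations.

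**Working it through.** The load is stated, not derived, so the plan has no calculation to reproduce. What can be checked is whether the stated load is compatible with the use made of the test.

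**Inputs from the documents**

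- Load: 75 mg (Section 5.2).
- Index: ΔC30/ΔG30 (Section 14.3).
- Glucose scale for comparison: the fasting goal of 110 mg/dL (Section 4.1).

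**Assumed inputs (not in the documents)**

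- Main range for the glucose distribution volume: 12 to 30 L, that is 120 to 300 dL.
- Wider range: body weight 60 to 150 kg and 0.15 to 0.25 L/kg, that is 9 to 37.5 L.
- Extreme case: the whole load confined to 3 L of plasma.

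**Formula.** The upper bound on the rise is load (mg) / volume (dL). It is generous, because it takes the whole load as absorbed at once with none cleared.

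| Volume assumed | Calculation | Largest possible rise |
|---|---|---|
| 12 L | 75 / 120 | 0.63 mg/dL |
| 30 L | 75 / 300 | 0.25 mg/dL |
| 9 L (60 kg × 0.15 L/kg) | 75 / 90 | 0.83 mg/dL |
| 20 L (100 kg × 0.20 L/kg) | 75 / 200 | 0.375 mg/dL |
| 37.5 L (150 kg × 0.25 L/kg) | 75 / 375 | 0.20 mg/dL |
| 3 L (plasma only) | 75 / 30 | 2.5 mg/dL |

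Outside the extreme case the largest value is 0.83 mg/dL, and 0.83 / 110 = 0.76% of the fasting goal. Even the plasma-only bound is 2.5 / 110 = 2.3%.

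**Consequence for each Aim 2 measure, if the text is followed literally**

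- **c-peptide index:** ΔG30 is close to zero, so the ratio is unstable.
- **oDI:** probably affected. Section 14.3 describes it as β-cell function relative to insulin sensitivity, which suggests a term from the OGTT response, but no formula confirms this.
- **1/fasting insulin:** unaffected, because it needs only the fasting sample.
- **A1c and total daily insulin dose:** unaffected.

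The primary outcome, percent change in BMI, does not use the test.

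**The case against.** The strongest reply is that nobody will give this amount. The paragraph describes a two-hour test in wide use with a standard ingestion, and Section 24.1 describes established research units with trained staff. A unit slip in one sentence does not show that any order set or worksheet carries it. This stands, and it limits the point to the procedure as written.

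Three stronger readings are tempting, but the documents do not support them.

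- **That the trial cannot produce its β-cell outcomes.** This would require staff to give the literal amount, and nothing in the documents shows that they do.
- **That the risk statement in Section 12.1 alone proves the load wrong.** Section 5.2 has participants withhold basal insulin for 36 hours or bolus insulin for 6 hours, and take their last metformin the evening before. Some hyperglycemia during testing could follow from that. The statement sits poorly with a 75 mg load but does not settle the matter.
- **That the word standard refers to the load used in the two earlier studies named in the paragraph.** One sentence says the OGTT was used in those studies, and a separate sentence describes the ingestion as standard. Neither gives the studies' load.

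It is also fair to object that the size of the rise rests on outside assumptions about volume. The conclusion is the same across the whole range shown. A further step, such as the probability that a measured rise is negative, would need an assay precision that the documents do not give, so none is claimed.

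**Conclusion.** The point holds as an internal inconsistency. The only load in the available text cannot be squared with an index that needs a measurable 30-minute glucose rise, nor easily with the description of the ingestion as standard. Over an assumed 12 to 30 L, the largest possible rise is about 0.63 to 0.25 mg/dL.

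The consequence is conditional and narrow. Followed literally, the procedure would spoil the c-peptide index and probably oDI. The other three Aim 2 measures and the primary BMI outcome would not change. The figure is most likely a slip in the unit, and the practical risk is small if staff follow a usual OGTT procedure. It still merits correction, because it stands in the one sentence that defines the test behind a secondary endpoint. Consent pages are not part of the available text, so whether they state a load is unknown.

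**What to change.** Reconcile the load in Section 5.2 with the rest of its paragraph, the risk statement in Section 12.1 and the Aim 2 outcomes in Section 14.3. Then confirm that the research-unit order set, worksheets and participant materials carry the same reconciled figure at baseline, week 24 and week 52. The amount is for the sponsor to settle; none is proposed here.

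The cost is a very small text correction and a document check. It adds no visits, samples or procedures, and it changes neither the sample size nor the analysis.

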**7.0 Sharing of Results with Participants**

7.1 The results of tests done during the study will be shared with participants upon request.

7.2 Sharing of genetic testing: Not applicable

**8.0 Study Population**

8.1 Inclusion Criteria:

- Ages 12 to  $\leq$  20 years at study entry
- Obesity (BMI  $\geq$  the 95th percentile for age and sex)
- HgbA1c  $\geq$  6.5% at type 2 diabetes diagnosis
- Negative diabetes auto-antibodies
- English-speaking
- For participants of child-bearing potential: when sexually active, agreement to use two forms highly effective contraception (oral contraceptive pill, IUD, implant, and/or condoms) during study participation

8.2 Exclusion Criteria:

- Pregnancy or lactation
- Newly-initiated or change in dose of weight altering medication within past 6 months, including SGLT-2 inhibitors, DPP-IV inhibitors, liraglutide 1.8 mg and exenatide ER
- Current or recent (< six months prior to enrollment) use of anti-obesity medication(s) defined as orlistat, phentermine, topiramate, combination

PHN/TPM, semaglutide, and/or combination naltrexone/bupropion (monotherapy use of naltrexone or bupropion is not an exclusion)

- Current use of sulfonylureas
- Previous metabolic/bariatric surgery
- Current use of a stimulant medication
- History of glaucoma
- Current or recent (<14 days) use of monoamine oxidase inhibitor or carbonic anhydrase inhibitors
- Known hypersensitivity to sympathomimetic amines
- Any history of treatment with growth hormone
- Any history of bulimia nervosa
- Major psychiatric disorder as determined by the local medical monitor
- Unstable and clinically-diagnosed (defined as documented in the medical record, if available) depression or PHQ-9 score  $\geq 15$
- Any history of active suicide attempt, a “yes” answer to Question 4 (Active Suicidal Ideation with Some Intent to Act, Without Specific Plan) on the “Suicidal Ideation” portion of the C-SSR, or a “yes” to answer to Question 5 (Active Suicidal Ideation with Specific Plan and Intent) on the “Suicidal Ideation” portion of the C-SSRS
- History of suicidal ideation or self-harm within the previous 30 days or a “yes” answer to any of the suicide-related behaviors (actual attempt, interrupted attempt, aborted attempt, preparatory act, or behavior) on the “Suicidal Behavior” portion of the C-SSRS and the ideation or behavior occurred within the past month.
- Current pregnancy or plans to become pregnant during study participation
- Current tobacco use
- ALT or AST  $\geq 3$  times the upper limit of normal
- Moderate (Child-Pugh score 7-9) or severe (Child-Pugh score 10-15)
- Bicarbonate  $<18$  mmol/L
- Moderate (creatinine clearance [CrCl] greater than or equal to 30 and less than 50 mL/min) or severe (CrCl less than 30 mL/min) renal impairment
- History of seizures (with the exception of febrile seizures)
- BP for ages 13 and older of  $\geq 130/80$  on 3 separate measurements and for age 12  $\geq 95$ th percentile on 3 separate measurements
- HR  $\geq 120$  bpm on 3 separate measurements
- History of structural heart defect or clinically significant arrhythmia
- Diagnosed monogenic obesity
- Any history of cholelithiasis
- Any history of nephrolithiasis
- Clinically diagnosed hyperthyroidism
- Untreated thyroid disorder or TSH below the lower laboratory limit of normal

- Any disorder, unwillingness, or inability, not covered by any other exclusion criteria, which in the investigator's opinion may put the participant at risk.

### 8.3 Visit Detail:

Screening Visit: After explaining the study in detail, written parental consent and assent will be obtained. If the participant is  $\geq 18$  years of age, the participant consent will be obtained. Potential participants will then undergo screening for inclusion and exclusion criteria (physical exam with height and weight for BMI calculation, Tanner staging for pubertal status. Screening lab [AST, ALT, INR, TSH, bilirubin, albumin, basic metabolic panel will be drawn at this visit and reviewed before setting up the baseline visit. INR, bilirubin, and albumin will be used to determine a Child-Pugh score for hepatic impairment for eligibility. Urine pregnancy test for participants of child-bearing potential will be obtained. BP and HR will be taken. Contraceptive counseling will be provided. The PHQ-9 and C-SSRS will then be completed. All other co-administered medications will be assessed. Participants will then have their medical and medication history collected and demographics collected.

Baseline Visit: Participants who meet eligibility criteria will return for a baseline visit within 4 weeks of the screening visit. Participants will have a physical examination, their height and weight will be measured and their blood pressure and heart rate will be taken. An EKG will be done, and contraceptive counseling will be given. Participants will complete the EDE-Q, and PedsQL. Their daily insulin and metformin doses will be reviewed if applicable. Participants will be instructed how to place and replace a CGM as well as swipe and upload data. The participant will have the OGTT testing and the plasma glucose levels, c-peptide levels and insulin levels taken at outlined timepoints as well as baseline lipid profile, and vitamin D level be drawn at time 0. Approximately 2 tablespoons of blood will be drawn at the visit. The participant will also have an iDXA for total body fat, visceral fat and bone mineral density calculations. Lifestyle management counseling will be given. The participant will then be randomized to receive either PHN/TPM or placebo and will be instructed on how to take the study medication. The participant will be provided with a Bluetooth scale for use at home and to transmit weights to the study team, with a water bottle to encourage water intake and with a drawstring bag to carry the study items.

Weeks 4, 8, 16, 20, 28, 32, 40, 44 and 48: At these timepoints the study staff will review the CGM data, and the participant may be contacted via telephone about adjusting their insulin or metformin dose. Participant will also present to the DCRU to collect study medication as well as upload CGM data if they are unable to do so from home and they will be given new CGM sensors. Monthly urine

pregnancy test results and contraceptive counseling if applicable will also be done when the patient collects their study medication. If participants are able to upload CGM at home, then after week 24, a 2-month supply of study drug and CGM sensors and 2 urine pregnancy tests will be given to participants at visit 24 and a 3-month supply of study medication and CGM sensors and 3 pregnancy tests will be given at visit 36. Study coordinator will then only do a telephone visit for weeks 28, 32, 40, 44, and 48 to review adverse events, home weight, and results of urine pregnancy test.

Week 12 and Week 36: Visits at these timepoints will be conducted at the CRU. Vital signs and weight will be collected. Participants will be asked about any adverse events they have experienced. Contraceptive and lifestyle management counseling will again be given and a pregnancy test will be performed. Participants will have a physical examination and pubertal assessment. Approximately one teaspoon of blood will be drawn for a hemoglobin A1c. Patients will also complete the EDE-Q, PHQ-9, and C-SSRS. Participants will be provided with new CGM sensors and study Medication bottles will be collected and pills counted by the study team to assess compliance. At the Week 12 visit, the pill count will be conducted by a team member not involved in the study so that the study blind is not broken.

Week 24 and Week 52: Participants will present for an in-person visit for a physical examination. Tanner staging, height and weight measurements will be collected. Vital signs (BP and HR) will also be collected. Contraceptive counseling and lifestyle management will again be given. Participants will be asked about adverse events that they have experienced. Blood will be drawn for a hemoglobin A1c, basic metabolic panel, lipid profile, and a Vitamin D 25. A review of the participants' daily insulin doses will be reviewed. Any co-administered medications will be discussed. Participants will have the OGTT testing and blood will be collected at the outlined timepoints for plasma glucose levels, c-peptide levels and insulin levels. Approximately two tablespoons of blood will be drawn at the visit. Participants will be asked to complete the EDE-Q, PedsQL, PHQ-9 and C-SSRS evaluations. Urine pregnancy test will be done and reviewed if applicable. An iDXA for total body fat, visceral fat and bone mineral density will be conducted. The participant will have their CGM data reviewed and new CGM sensors will be provided at week 24. The participant's insulin dose will be reviewed and their adherence to the study medication will be assessed. Study medication will be distributed for week 24. Instructions on how to down-titrate off the study medication will be done on week 52. Participants who elect to upload their CGM data remotely before the visit may elect to receive study medication, home urine pregnancy tests, and sensors to last them for the remainder of the study.

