## 5.0 Procedures Involved

### 5.1 Study Design:

This is a pilot, pragmatic, randomized trial with 6-month placebo-controlled period followed by a 6-month open label extension. Thirty pubertal or post-pubertal adolescents will be randomized into one of two arms:

- PHN/TPM
- Placebo

MEDICAL PROTOCOL PEDS-2021-29785

PROTOCOL TITLE: Phentermine/Topiramate in Adolescents with Type 2 Diabetes and Obesity

VERSION DATE: 10Dec2024

Participants will engage in typical T2D clinical care and lifestyle management, with the addition of PHN/TPM or placebo therapy for 6 months followed by a 6-month open label extension during which all participants will be given PHN/TPM in an unblinded fashion.

The schedule of events (below) shows the data that will be collected at each study visit.

MEDICAL PROTOCOL PEDS-2021-29785

PROTOCOL TITLE: Phentermine/Topiramate in Adolescents with Type 2 Diabetes and Obesity

VERSION DATE: 10Dec2024

Schedule of Events

Week	Screening	Baseline	Placebo-Controlled												
	-4%	0%	4	8	12%	16	20	24%	28	32	36%	40	44	48	52%
Informed consent/assent	X														
Demographics	X														
Medical and medication history	X														
Review of inclusion/exclusion criteria	X														
Randomization		X													
Urine pregnancy test d	X	X	X	X	X	X	X	X	X	X	X	X	X	X	X
Physical Exam	X	X			X			X			X				X
Tanner staging	X				X			X			X				X
Anthropometrics a	X	X	X	X	X	X	X	X	X	X	X	X	X	X	X
Vital signs (Blood pressure and heart rate)	X	X			X			X			X				X
EKG		X													
Contraceptive counseling	X	X	X	X	X	X	X	X	X	X	X	X	X	X	X
Adverse events			X	X	X	X	X	X	X	X	X	X	X	X	X
Hemoglobin A1c		X			X			X			X				X
Eating Disorder Examination Questionnaire (EDE-Q)		X			X			X			X				X
Peds-QOL (general and diabetes modules)		X						X							X
Patient Health Questionnaire (PHQ-9)	X				X			X			X				X
Columbia-Suicide Severity Rating Scale (C-SSRS)	X				X			X			X				X
Total daily insulin dose assessment		X			X			X			X				X
Oral Glucose Tolerance Test (OGTT)		X						X							X
ALT, AST, INR, TSH, bilirubin, albumin, basic metabolic panel	X							X							X
Lipid profile, vitamin D 1,25 b		X													
Plasma glucose level b		X						X							X
c-peptide level b		X						X							X
Insulin level b		X						X							X
iDXA (visceral and total body fat and bone mineral density)		X						X							X
Review of CGM data c			X	X	X	X	X	X	X	X	X	X	X	X	X

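### No eligibility re-check, and no repeat C-SSRS, is specified at the Baseline visit before randomisation

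*Combined protocol and SAP*

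**What the plan says.** Section 5.1, Schedule of Events, has a row "Review of inclusion/exclusion criteria" with a mark at Screening (Week -4) and none at Baseline (Week 0). PHQ-9 and C-SSRS follow the same pattern and are next marked at Week 12. Randomisation and the first dispensing of study drug are marked at Baseline.

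Section 8.3 treats eligibility as settled before the second visit: "Participants who meet eligibility criteria will return for a baseline visit within 4 weeks of the screening visit". After the baseline procedures it continues: "The participant will then be randomized to receive either PHN/TPM or placebo and will be instructed on how to take the study medication".

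Section 8.2 excludes anyone with "History of suicidal ideation or self-harm within the previous 30 days", and puts a similar one-month limit on suicidal behaviour reported on the C-SSRS. The date from which the 30 days are counted is not given. The blood pressure and heart rate exclusions each need three readings; for heart rate the wording is "bpm on 3 separate measurements".

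On the EKG, Section 8.3 puts it at Baseline ("An EKG will be done, and contraceptive counseling will be given"), as does the schedule, while Section 5.2 says "Electrocardiogram will be performed at screening/baseline visit and per PI discretion".

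**The concern.** Up to four weeks separate the only scheduled eligibility review from randomisation. For most exclusions this matters little, because they concern fixed history or because the relevant measurement is taken again at Baseline. It matters for suicidality: the exclusion is time-limited, the instrument that measures it is not repeated, and Section 12.1 itself names suicidal ideation and behaviour as a risk of topiramate.

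Two things are at stake. The first is safety: someone whose status changed after Screening could be randomised because no step requires anyone to ask. The second is interpretation. Without a C-SSRS at the start of treatment, ideation that arose between Screening and the first dose may first be captured by that instrument at Week 12 and be read as an on-treatment event. Under Section 17.2 suicidal ideation leads to removal from the study. Section 11.3 ends data collection on withdrawal, and Sections 14.1 and 14.4 keep the participant in the intention-to-treat analysis with the last value carried forward. A case that could have been a screen failure would therefore become a randomised participant with a truncated record.

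**Working it through.** **The plan's own figure.** The plan gives no number for this point. Its only design calculation, in Section 14.2, is unaffected. With SD 8.9, correlation 0.75, 15 per arm, a two-sided test at 0.05 (two-sided is assumed), 80% power and a normal approximation:

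- adjusted SD = 8.9 × √(1 − 0.75²) = 5.887
- detectable difference = (1.960 + 0.842) × 5.887 × √(2/15) = 6.02%, against the stated 6%
- with 13.5 per arm (10% attrition): (1.960 + 0.842) × 5.887 × √(2/13.5) = 6.35%, against the stated 6.3%

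**What is scheduled before the first dose** (Section 5.1, Schedule of Events):

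| Item | Screening | Baseline | Next |
|---|---|---|---|
| Inclusion/exclusion review | yes | no | none |
| C-SSRS | yes | no | Week 12 |
| PHQ-9 | yes | no | Week 12 |
| Physical exam | yes | yes | Week 12 |
| Vital signs | yes | yes | Week 12 |
| Urine pregnancy test | yes | yes | Week 4 |
| Co-administered drug review | yes | yes | Week 12 |
| EKG | no | yes | none |
| Randomisation | no | yes | none |
| Dispensing of study drug | no | yes | Week 4 |

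Most of the information needed is thus collected by Baseline. The exceptions that bear on a dated exclusion are the C-SSRS and, less clearly, the PHQ-9.

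**Share of the suicidality look-back left unassessed.** Let g be the days from Screening to Baseline, at most 28 (Section 8.3). Count the 30-day window (Section 8.2) back from randomisation. The share that falls after the Screening assessment is min(g, 30)/30:

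- g = 7: 7/30 = 23%
- g = 14: 14/30 = 47%
- g = 21: 21/30 = 70%
- g = 28: 28/30 = 93%

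**Interval between C-SSRS assessments.** Week -4 to Week 12 is 4 + 12 = 16 weeks at the maximum gap, with the first dose in between.

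**Schedule against visit text.** The baseline paragraph of Section 8.3 places the exam, vital signs and EKG before randomisation. It omits the pregnancy test and the co-administered drug review that the schedule marks at that visit, mentioning only insulin and metformin doses. It contains no sentence that applies any baseline result to Section 8.2. The participant-safety text in Section 17.2 likewise places adherence to the criteria at screening.

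**Blood pressure and heart rate.** Sections 5.2 and 8.3 do not say how many readings are taken per visit. With one per visit (an assumption), two exist by randomisation; with three at Screening, all exist. The plan does not say which applies.

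**The case against.** The strongest reply is that no text tells staff to randomise someone known to be ineligible. The exclusions in Section 8.2 are not, in general, confined to the screening date, and the last of them leaves room for the investigator's judgement. Section 12.7 records adverse events from consent onward and has staff ask about them at each in-person visit, and Baseline is one. Section 12.1 adds monthly adverse-event review and monitoring for suicidality. All of this stands, and it limits the harm. It does not replace the missing step: the adverse-event row of the schedule starts at Week 4, and a general enquiry is not the instrument on which the exclusion is partly defined.

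Several stronger readings are tempting but not supported:

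- *That time-limited exclusions go unverified at randomisation.* Pregnancy test, drug review, exam, vital signs and EKG are all scheduled at Baseline. What is absent is a stated rule for using them.
- *That an EKG exclusion is missed.* Section 8.2 excludes arrhythmia by history and sets no EKG threshold.
- *That only two of three blood pressure and heart rate measurements can exist.* This rests on one reading per visit, which the plan does not say.
- *That the PHQ-9 exclusion lapses.* Section 5.2 ties the cut-off of 15 to the screening visit, so not repeating it is consistent with the plan.
- *That the gap is 119 days.* The sum 28 + 84 + 7 = 119 is correct for the longest interval between C-SSRS assessments, but 84 + 7 = 91 of those days follow the first dose. A baseline C-SSRS would close only the other 28. The 42-day titration has no bearing on eligibility.
- *That each case costs 1/15 of an arm.* That is the weight of one participant, not an estimate of how often this happens. The documents give no rate.

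**Conclusion.** The point holds in a limited form and is worth correcting. No eligibility confirmation is specified between the Screening review and randomisation, and the C-SSRS is not repeated before the first dose. At the maximum gap, 28 of the 30 days before randomisation (93%) have no structured suicidality assessment; at shorter gaps the share falls in proportion. This assumes that the window is counted back from randomisation. If it is counted back from Screening, the exclusion is met on its own terms, but the interval before dosing is still unassessed by C-SSRS and there is no true pre-treatment reference.

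For the other baseline measurements the finding is narrower: they are scheduled, but their use for eligibility is not stated, and the schedule, Section 5.2 and Section 8.3 do not fully agree. How many participants would be affected cannot be estimated from the documents. Sample size and error rates do not change.

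**What to change.** 1. In the Schedule of Events, mark the inclusion/exclusion review and the C-SSRS (since-last-visit form) at Baseline. The PHQ-9 could be added alongside, but is optional.
2. In Section 8.3, state that randomisation follows a documented check of the C-SSRS, pregnancy test, vital signs, EKG and co-administered drug review against Section 8.2. Add the pregnancy test and drug review to the baseline paragraph.
3. In Section 8.2, give the date from which the 30-day and one-month look-backs are counted.
4. State by which visit the three blood pressure and heart rate measurements are obtained.
5. Reconcile the EKG timing in Section 5.2 with the schedule and Section 8.3.

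The cost is protocol wording and a few minutes with an instrument already in use. The downside is possibly a few more screen failures at Baseline, after some visit effort has been spent. The gains are a check at the point of randomisation and a pre-treatment suicidality reference for the safety tables.
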